11 TOXICITIES/SIDE EFFECTS

- **11.1** Information regarding the definition and reporting of adverse events, including serious adverse events, is provided in Section 17.2.
- 11.2 Hu3F8-BsAb is expected to be associated with the known side effects of m3F8 and hu3F8

Common side effects: pain, paresthesia, hypertension, hypotension, sympathetic neuropathy, presyncope, syncope, tachycardia, urticaria, pruritus, flushing, fever, somnolence, nausea, and emesis.

Less common side effects: diarrhea, serum sickness, hyponatremia, airway constriction, peripheral neuropathy, impaired accommodation of the eye, poor reactivity of pupils to light, transaminitis.

Rare but serious side effects: anaphylaxis, posterior reversible encephalopathy syndrome (PRES)

11.3 Cytokine release syndrome (CRS) has been reported in patients with B cell leukemia or lymphoma treated by anti-CD19 T cell immunotherapies (e.g. blinatumomab, anti-CD19 CAR-modified T cells). CRS correlated with anti-tumor efficacy, and the incidence, severity, and onset of CRS depend on therapeutic agents, cancer type, tumor burden, and patient's immune system.^{64,65,67,79,86-89} Severe cytokine release syndrome is characterized by fever (\geq 3days), elevation of serum cytokines, and clinical toxicities (hypotension, hypoxia, neurological symptoms). In NB patients, 19 patients were treated by anti-GD2 CAR-modified T cells therapy in a phase I study and severe CRS was not observed.⁹⁰ In adults, severe CRS is characterized by hypotension, respiratory distress and cardiac changes including arrhythmias, acute coronary syndrome, and impaired LV function, and neurological symptoms such as seizures. Instead of grading CRS according to CTCAE 4.0, CRS will be graded using the CRS revised grading system by Lee et al.⁹¹ described below in Table 8.

Grade	Toxicity
Grade 1	Symptoms are not life-threatening and require symptomatic treatment only, e.g. fever, nausea, fatigue, headache, myalgias, malaise
Grade 2	Symptoms require and respond to moderate intervention Oxygen requirement < 40% or Hypotension responsive to fluids or low dose of one vasopressor or Grade 2 organ toxicity

Table 8CRS revised grading system91

[figure not shown]
Grade	Toxicity	
Grade 3	Symptoms require and respond to aggressive intervention	
	Oxygen requirement $\geq 40\%$ or	
	Hypotension requiring high dose for \geq 3 hours * or multiple vasopressors or	
	Grade 3 organ toxicity or Grade 4 transaminitis	
Grade 4	Life-threatening symptoms	
	Requirement to ventilator support or	
	Grade 4 organ toxicity (excluding transaminitis)	
Grade 5	Death	

*High dose vasopressors are defined as follows: dopamine > 10 ug/kg/min; norepinephrine > 0.1 ug/kg/min; epinephrine> 0.1 ug/kg/min; or dobutamine> 10 ug/kg/min.

11.3.1 Management of Cytokine release syndrome

The following algorithm will be used if severe cytokine release syndrome occurs.

[figure not shown]

11.4 Neurotoxicity is another side effect of blinatumomab or anti-CD19 CAR-modified T cells. It was rare (< 5%) in children compared to adult patients in blinatumomab clinical studies.⁶⁷ Pathophysiology of the neurological toxicity is not clear; it could be related to CRS or could be associated with leukemic cells in CNS, hence it is unclear whether this is restricted to CD19 targeting immunotherapies or not.^{64,65} In the phase I study of anti-GD2 CARmodified T cells mentioned in Section 11.3, no patients developed neurological symptoms.⁹⁰ In addition to CRS, patients treated with hu3F8-BsAb may develop neurological toxicities due to adverse events of opiate analgesics, posterior reversible encephalopathy syndrome (PRES) which has been described with m3F8 and hu3F8.^{64-66,79} Patients who develop abnormal neurological symptoms need to be evaluated immediately and appropriate management should be instituted as soon as possible. This can include discontinuation of opiates, naloxone, management of hypertension and head imaging.

[figure not shown]
11.4.1 Management of Neurological toxicities

The following algorithm will be used for the management of neurotoxicity.

Grade 4 seizure, encephalopathy, depressed level of consciousness, or somnolence will require discontinuation of the hu3F8-BsAb. Except in the case of paresthesia, patients experiencing any grade 3 neurotoxicity (e.g. depressed level of consciousness, encephalopathy or somnolence) and patients with uncontrolled seizures will be considered as having DLT and not receive subsequent doses of hu3F8-BsAb. If parasthesia resolves to <grade 3 within 48 hours it will not be considered a DLT and patient may continue to receive protocol treatment if all eligibility criteria are met. In addition, if patients experience seizures, at least 72 hours should elapse before the next dose of hu3F8-BsAb is administered.

11.5 Management of Orthostatic Hypotension

11.6 If treatment is stopped due to toxicity, treatment may resume once the patient returns to meeting eligibility criteria as described in Section 6.

12 CRITERIA FOR THERAPEUTIC RESPONSE/OUTCOME ASSESSMENT

- **12.1** Response duration is calculated from first day of treatment with hu3F8-BsAb.
- **12.2** Patients are considered a response failure under this protocol if progressive disease is evident at any time.
- **12.3** Disease response for NB will use the revised International NB Response Criteria⁹²:
- **12.3.1** Overall Response:

Overall response will be defined by combining response of the individual components (i.e. soft tissue, bone, and bone marrow disease) (See 12.3.2-12.3.4).

- Complete response/remission (CR): All components meet criteria for CR.
- Partial response/remission (PR): PR in as least one component and all other components are either CR, minimal disease (MD) (bone marrow), PR (soft tissue or bone), or not involved (NI)*; no component with progression disease (PD).
- Mixed response (MR): PR or CR in at least one component but at least one other component with stable disease (SD); no component with PD.
- Stable disease (SD): SD in one component with no better than SD or NI* in any other component; no component with PD.
- Progressive disease (PD): Any component with PD.

*NI – Site not involved at study entry and remains uninvolved.

- **12.3.2** Primary (soft tissue) Tumor Response:
 - CR: <10mm residual soft tissue at primary site AND Complete resolution of MIBG or FDG-PET uptake (for MIBG-nonavid tumors) at primary site.
 - PR: ≥30% decrease in longest diameter of primary site AND MIBG or FDG-PET uptake at primary site stable, improved, or resolved.
 - PD: >20% increase in longest diameter taking as reference the smallest sum on study (this includes the baseline sum if that is the smallest on study) AND Minimum absolute increase of 5mm in longest dimension.
 - SD: Neither sufficient shrinkage for PR or sufficient increase for PD at the primary site.
- **12.3.3** Tumor Response at Metastatic Soft Tissue and Bone Sites:
 - CR: Resolution of all sites of disease, defined as: Nonprimary target and nontarget lesions measure <10mm AND Lymph nodes identified as target lesions decrease to a short axis <10mm AND MIBG uptake or FDG-PET uptake (for MIBG-nonavid tumors) of nonprimary lesions resolves completely.
 - PR: ≥30% decrease in sum of diameters of nonprimary target lesions compared with baseline AND all of the following:

Nontarget lesions may be stable or smaller in size AND No new lesions AND \geq 50% reduction in MIBG absolute bone score (relative MIBG bone score \geq 0.1 to \leq 0.5) or \geq 50% reduction in number of FDG-PET-avid bone lesion

• PD: Any of the following:

Any new soft tissue lesion detected by CT/MRI that is also MIBG avid or FDG-PET avid

Any new soft tissue lesion seen on anatomic imaging that is biopsied and confirmed to be neuroblastoma or ganglioneuroblastoma

Any new bone site that is MIBG avid

A new bone site that is FDG-PET avif (for MIBG-nonavig tumors) AND has CT/MRI findings consistent with tumor OR has been conferment histologically to be neuroblastoma or ganglioneuroblastoma

>20% increase in longest diameter taking as reference the smallest sum on study (this includes the baseline sum if that is the smallest on study) AND minimum absolute increase of 5mm in sum diameters of target soft tissue lesions

Relative MIBG score ≥ 1.2

- SD: Neither sufficient shrinkage for PR or sufficient increase for PD of nonprimary lesions.
- **12.3.4** Bone Marrow Metastatic Response:
 - CR: Bone marrow with no tumor infiltration on reassessment, independent of baseline tumor involvement.
 - PD: Any of the following:

Bone marrow without tumor infiltration that becomes >5% tumor infiltration on reassessment OR

- Bone marrow with rumor infiltration that increases by > two-fold and has >20% tumor infiltration on reassessment.
- MD: Any of the following:

Bone marrow with \leq 5% tumor infiltration and remains >0 to \leq 5% tumor infiltration on reassessment OR

Bone marrow with no tumor infiltration that has \leq 5% tumor infiltration on reassessment OR

Bone marrow with >20% tumor infiltration that has >0 to \leq 5% tumor infiltration on reassessment

- SD: Bone marrow with tumor infiltration that remains positive with >5% tumor infiltration on reassessment but does not meet CR, MD, or PD criteria.
- **12.4** Disease response for non-neuroblastoma tumors will use the Response Evaluation Criteria in Solid Tumor (RECIST) Version 1.1.
- **12.4.1** Measurable Disease:

The presence of at least one lesion that can be accurately measure in at least one dimension with the longest diameter at least 20 mm or lesions at least 10 mm on spiral scan is considered measurable disease.

- **12.4.2** Response Criteria
 - Complete Response (CR): Disappearance of all clinical and radiological evidence of target lesions.
 - Partial Response (PR): A greater than or equal to 30% decrease in the sum of the longest diameter of all index lesions in reference to the baseline sum of the longest diameters of the index lesions.
 - Stable Disease (SD): Response that is neither sufficient decrease to qualify as PR nor sufficient increase to qualify as Progressive Disease (PD).

- Progressive Disease (PD): A greater than or equal to 20% increase in the sum of the longest diameters of all index ("target") lesions, taking as reference the smallest sum of the longest diameters recorded at or following baseline OR the appearance of one or more new site of disease.
- 12.5 Pseudoprogression (tumor growth from immune response rather than true disease progression) can be seen in early time points after T-cell mediated immunotherapy. If pseudoprogression is suspected, patients will be followed clinically and/or by scans about 4 weeks later to determine if patient has true PD
- **12.6** Adequacy of trial: All patients who fulfill the eligibility requirements and complete the first cycle of hu3F8-BsAb will have an adequate trial and are considered evaluable for protocol.

In phase I, patients will be considered evaluable if patients develop progressive disease after completing protocol treatment during cycle 1 but do not receive any other treatment before Day 28 of the DLT observation period.

13 CRITERIA FOR REMOVAL FROM STUDY

- **13.1** Patients come off treatment if there is PD at any time. Best clinical judgment will be used to determine whether a patient must undergo tests between cycles to make sure disease is not progressing. Patients are followed for toxicities for 30 days from last treatment.
- 13.2 Patients come off treatment if they have DLT (during cycle 1 of phase I) or life-threatening toxicity clearly attributable to hu3F8-BsAb. Patients in the first stage of phase I (one patient per dose level cohort) who experience ≤ grade 2 toxicity, will not come off treatment but can continue at the same dose if they do not experience DLT and if toxicity subsides to <grade 2 within 35 days of dose 1 of Hu3F8-BsAb.

- **13.3** Patients who become pregnant during the study must be withdrawn from treatment
- **13.4** The investigators will make every reasonable effort to keep each patient in the study until all planned treatments and assessments have been performed. The investigators may discontinue study drug treatment for the following reasons:
 - Adverse events, including unacceptable toxicity or exacerbation of underlying disease, associated with study drug administration and necessitating discontinuation of treatment. Patients who are coming off treatment due to adverse events will be treated and followed according to established, acceptable medical practice. All pertinent information concerning the outcome of such treatment will be entered in the MSKCC institutional Clinical Research Database (CRBD). Patients will be followed until resolution or stabilization of the adverse event.

13.5 Off Study Criteria:

- Thirty days after the last dose of study drug for patients coming off treatment due to DP
- For patients coming off treatment due to adverse events, patients will be followed until the date the event returns to baseline or <Grade 3 (whichever is higher) or the date patients start another treatment, whichever is earlier.
- Death
- Lost to follow-up
- Withdrawal of consent. The patient's desire to withdraw from the study may occur at any time. The investigator should carefully consider whether the patient's withdrawal of consent is due to an adverse event, and if so, record the adverse event as the reason for withdrawal.
- Withdrawal by the physician for clinical reasons not related to study drug treatment in the absence of an adverse event.
- Violation of the study protocol, including failure to return for required treatments or assessments. Patients who fail to return for treatments will be included into the study assessment if they receive at least one dose of hu3F8-BsAb.

14 **BIOSTATISTICS**

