2.2 Phase II

Primary Objectives:

• In Group 1: Assess the overall response rates of hu3F8-BsAb in patients with relapsed or refractory NB.

In Group 2: Assess the progression free survival (PFS) in patients with relapsed or refractory osteosarcoma at 4 months from the first hu3F8-BsAb treatment.

Secondary Objectives:

- To evaluate the duration of complete remission in groups 1 and 2.
- In Group 2: Assess the overall response rates of hu3F8-BsAb in patients with relapsed or refractory osteosarcoma.
- To continue to assess the safety/toxicity of hu3F8-BsAb.
- To evaluate HAHA.

Exploratory Objectives:

- To assess overall survival (OS) and PFS after treatment with hu3F8-BsAb.
- To study immunological effects of hu3F8-BsAb
- To study the effects of hu3F8-BsAb on BM DNA and RNA (Neuroblastoma patients only).
- To study the effects of stool microbiome of the activity of hu3F8-BsAb.

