2.6. Exploratory Efficacy Variable(s)

2.6.1. Phase II

2.6.1.1. Overall Survival (OS)

OS will be defined as the time from the first dose of treatment to the time of death or last follow up known to be alive for patient without death date.

For patients who have not died, overall survival will be censored at the date of last contact (date the patient was last known to be alive).

OS (in months) = [date of event or censoring – First dose of treatment + 1]/30.4375.

OS will be calculated with one decimal.

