6.6.3.3. OS for Phase I

OS analyses will be performed in patients from the FAS.

The number of overall censored patients, number of patients with events and Kaplan-Meier estimates median time will be provided with 25th percentile and 75th percentile and 95% Confidence Interval.

In addition, the results will be presented graphically in Kaplan-Meier plots including count for numbers of patients at risk.

In addition, OS rates at different time points (every 6 months) will be estimated with corresponding 2-sided 95% CIs.

Frequency (number and percentage) of patients with an event (death) and censoring reasons will be presented by treatment group. Censoring reasons are as follows:

- Alive
- Withdrawal of consent
- Lost to follow-up

Lost to follow-up will include patients that the investigator states were lost to follow-up prior to the analysis cut-off.

OS values will be also presented in a data listing.

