6.6.6. Exploratory Analysis

6.6.6.1. OS for Phase II

OS is defined as the time from first dose of treatment until death from any cause. All deaths will be included, whether they occur during the trial or following treatment discontinuation.

Data will be presented by cancer type (NB versus Osteosarcoma) based on the FAS.

The number of overall censored patients, number of patients with events and Kaplan-Meier estimates median time will be provided with 25th percentile, 75th percentile and 95%

Confidence Interval. In addition, the results will be presented graphically in Kaplan-Meier plots including count for numbers of patients at risk.

In addition, OS rates at different time points (every 6 months) will be estimated with corresponding 2-sided 95% CIs.

Frequency (number and percentage) of patients with an event (death) and censoring reasons will be presented by treatment group. Censoring reasons are as follows:

- Alive
- Withdrawal of consent
- Lost to follow-up

Lost to follow-up will include patients that the investigator states were lost to follow-up prior to the analysis cut-off.

OS values will be also presented in a data listing.

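### Protocol 13.5 ends follow-up 30 days after the last dose at progression, yet the SAP asks for 6-monthly overall survival; as written, OS is likely to be informatively censored

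*Protocol*

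**What the plan says.** **Leaving the study.** Protocol 13.5 removes a patient whose treatment stops for progression "Thirty days after the last dose of study drug for patients coming off treatment due to DP". For a stop due to an adverse event, "patients will be followed until the date the event returns to baseline or <Grade 3 (whichever is higher) or the date patients start another treatment" (the earlier of the two applies).

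**What is collected afterwards.** The follow-up columns of Protocol Tables 6 and 7 hold one item, HAHA blood, for up to 5 years but ending when the patient is off study. Under Protocol 10.17, scans after cycle 4 continue only while the patient is on study. Section 17.2.4.3 asks for possibly related SAEs and secondary malignancies during follow-up, not vital status.

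**What the analysis needs.** OS is a secondary variable in Phase I (SAP 2.5.1.5). In Phase II it is an exploratory objective: "To assess overall survival (OS) and PFS after treatment with hu3F8-BsAb" (Protocol 2.2). SAP 6.6.6.1 states for Phase II: "All deaths will be included, whether they occur during the trial or following treatment discontinuation". In both phases "OS rates at different time points (every 6 months) will be estimated with corresponding 2-sided 95% CIs" (SAP 6.6.3.3, repeated in 6.6.6.1). For survivors, "overall survival will be censored at the date of last contact (date the patient was last known to be alive") (SAP 2.6.1.1). The censoring reasons to be tabulated are alive, consent withdrawn and lost to follow-up; none covers removal under 13.5.

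**Group 2 primary endpoint.** SAP 2.4.2.2 censors PFS at the last adequate scan. A patient with no post-baseline scan is censored on the first treatment date, unless death occurs by the time of the cycle 4 scan. All treated patients stay in the FAS (SAP 6.6.1.2).

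**The concern.** Kaplan-Meier OS is valid only if patients who are censored have the same later risk of death as those still followed. Under 13.5 the event that triggers censoring is progression, the strongest marker of approaching death in relapsed neuroblastoma or osteosarcoma. If follow-up really stops there, the curve leans towards survival among patients who have not yet progressed, and most deaths are never seen. The SAP's censoring table would not reveal this, because it has no category for these patients.

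The second strand concerns the Group 2 primary endpoint. The first scan falls after the second dose of cycle 2. A patient stopped for toxicity in cycle 1 whose event settles quickly can be off study before then. Such a patient counts in the FAS but adds nothing to the 4-month estimate, and in a group of 18 a few of these matter.

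**Working it through.** **1. The plan's own figure.** The documents give no figure for OS bias, but they do give Group 2 power: 90% for n = 18, 12% against 40%, one-sided 95% Wilson interval. The lower limit is [p + z²/2n − z√(p(1−p)/n + z²/4n²)] / (1 + z²/n), with z = 1.645. At 4/18 it is 0.104 and at 5/18 it is 0.142, so success needs at least 5 of 18. Exact binomial power at 40% is 0.906 and the type I error at 12% is 0.056. The stated power reproduces; sample-size arithmetic is not at issue.

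**2. OS if data collection stops at off-study.** Simulation of 400,000 patients per scenario.

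From the documents:
- 4-month PFS of 12% or 40% (Group 2 null and alternative, used here as illustrations), giving an exponential rate of −ln(PFS)/4 per month.
- Doses on days 1 and 8 of 28-day cycles.
- Off study 30 days after the last dose before progression, or at progression if that is later.

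Assumed, because the documents do not give them:
- Median post-progression survival of 6 or 12 months, exponential.
- 0, 2, 5 or 10% of PFS events being deaths without progression, all of them captured.
- Dosing every 28 days until progression (in Phase II the gap after cycle 4 may be longer).
- No death found after off-study.

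True 12-month OS against the Kaplan-Meier estimate:

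| Deaths without progression | 12% PFS, 6 mo | 12% PFS, 12 mo | 40% PFS, 6 mo | 40% PFS, 12 mo | Excess (points) |
|---|---|---|---|---|---|
| 0% | 32 vs 67 | 56 vs 82 | 44 vs 83 | 65 vs 91 | +26 to +39 |
| 2% | 31 vs 61 | 55 vs 75 | 43 vs 79 | 63 vs 87 | +20 to +36 |
| 5% | 30 vs 53 | 53 vs 64 | 42 vs 74 | 62 vs 81 | +11 to +32 |
| 10% | 29 vs 43 | 51 vs 52 | 40 vs 66 | 59 vs 72 | +1 to +26 |

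Across the table, 5 to 18% of the deaths within 36 months are observed.

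**3. Where the sign changes.**
- With a post-progression median of 18 months, 10% deaths without progression and 4-month PFS of 12%, true 12-month OS is 61% and the estimate is 55%.
- If deaths after off-study are found but survivors' last-alive dates stay frozen at off-study, the estimate falls below the truth: 33% against 40% (4-month PFS 40%, post-progression median 6 months, 10% deaths without progression, data cut-off assumed uniform between 6 and 36 months).

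**4. How much data the 12-month point would rest on.** In the 10% scenarios, about 0.3% of patients (4-month PFS 12%) or 7.7% (4-month PFS 40%) are still at risk at 12 months. At the planned sizes, the more favourable case gives 0.077 × 18 = 1.4 patients in Group 2 and 0.077 × 30 = 2.3 in Group 1.

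**5. Toxicity stops in Group 2.** Suppose k of 18 patients are censored on day 1. As a proxy for the Kaplan-Meier interval, apply the Wilson rule to 18 − k.
- If the censoring is unrelated to outcome: k = 1 gives power 0.874. For k = 2 the limit at 4/16 is 0.118 and at 5/16 is 0.161, so 5 of 16 are needed and power is 0.833. Beyond that, power moves in steps because the required count drops: k = 4 needs 4 of 14, with power 0.876 but type I error 0.077.
- If every censored patient would in fact have failed: a true 40% reads as 0.40 × 18/16 = 45% for k = 2 and 0.40 × 18/14 = 51% for k = 4. A true 12% reads as 13.5% and 15.4%.

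**The case against.** The strongest reply is that the SAP presumes survival status is known. It counts deaths after treatment stops in Phase II, censors at the date last known alive rather than at progression, and lists only censoring reasons that fit continued follow-up. The trial recruits at one centre, where deaths may come to notice anyway. Protocol 13.4 adds that "The investigators will make every reasonable effort to keep each patient in the study until all planned treatments and assessments have been performed". The eCRF is not among the documents supplied, so a survival form cannot be excluded. This much stands: a reader might infer that OS will be badly biased upward, and the documents do not support that as a certainty. The size depends on post-progression survival and on deaths without progression, neither of which they give, and the direction depends on what is found after off-study.

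What does not stand is the idea that the intention to count deaths supplies them. 13.5 and the follow-up columns are what the site works from, and they contain no survival contact. Retention effort under 13.4 pulls against 13.5 and sets no schedule. Ad hoc discovery of deaths is not a safe substitute, since step 3 shows that it can bias the curve the other way.

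A reader might also infer that toxicity stops are lost to the Group 2 primary endpoint. They are not: they remain in the FAS, any adequate scan already obtained counts, and a death by the cycle 4 scan counts for those with no scan. Protocol 11.6 lets treatment resume after a toxicity stop, and the SAP would censor at new anti-cancer therapy whatever 13.5 said. The effect is therefore modest and confined to patients who leave before a scan.

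Two further points limit the stakes. Numbers at risk and confidence intervals will be shown, so the thinness of late OS estimates would be visible, although its cause would not. The HAHA Cox analysis in SAP 6.6.3.6.1 is described for OS and PFS up to 4 months, so the 12-month figures should not be carried over to it.

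**Conclusion.** The conflict is real: 13.5 ends participation shortly after progression and provides no survival contact, while the SAP asks for OS at 6-monthly time points in both phases. If data collection stops at off-study, the censoring is informative and OS is likely to be overstated. The excess at 12 months is about 11 to 39 points with 0 to 5% deaths without progression and a post-progression median of 6 to 12 months, and 1 to 26 points with 10%. It can reverse with longer post-progression survival, or if late deaths are found without updating survivors' dates. OS is secondary in Phase I and exploratory in Phase II and drives no success rule, so this threatens interpretation rather than the trial's decision. For the Group 2 primary endpoint the effect is smaller: two day-1 censorings cut power from about 0.91 to about 0.83, or make a true 40% read as 45% if both patients would have failed. The documents give no expected number of such patients.

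**What to change.** In Protocol 13.5, separate end of treatment from end of follow-up, and then:

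- Collect vital status by chart review or telephone for every treated patient to a stated common cut-off, updating the last-alive date for survivors as well as recording deaths. The 5-year limit in the protocol belongs to HAHA blood and lapses at off-study, so it cannot serve as the survival cut-off without being restated.
- Keep Group 2 patients who stop without progression on the scans already scheduled, through the 4-month scan.

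The cost is one amendment paragraph and a small amount of existing coordinators' time.

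If survival status cannot be collected, there are two ways out. One is to amend the Phase II OS objective in Protocol 2.2 and section 14.3.1 together with the SAP; deleting OS from the SAP alone would contradict both. Protocol 14.1.2.2, which uses OS in Phase I, would need the same treatment. The other is to label the OS curve as limited to on-study follow-up and drop the 6-monthly rates.
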